3.1.3 Inclusion Criteria

All HIV adult patient (≥ 18 years) on first-line ART will be screened for eligibility at the health care facility serving the two communities. The eligibility criteria will include:

- All adult patients who are stable. To be considered “stable” a patient must:
 1. Be on first line treatment for more than 6 months and retained in care
 2. Must be virologically suppressed (according to the current standard of care definition of viral suppression)
 3. WHO stage I and II at the time of screening
- Patient resides within the clinic catchment area
- Willing to provide written informed consent and accept CHiPs intervention.

3.1.4 Randomization

The community zones will be randomized by the research team to one of the three arms:

1. Arm 1 – Patients residing in these zones will be offered a choice of being part of an Adherence club or to continue to receive care at the clinic
2. Arm 2 – Patients residing in these zones will be offered a choice of Home ART delivery by the CHiP or to continue receiving care at the clinic
3. Arm 3- Patients residing in these zones will continue receiving care at the clinic (control arm).

Across the two communities (Chipata and Kanyama), there are 104 community zones that will be randomized to one of the three arms above.

Community	Total number of zones	Arm 1	Arm 2	Arm 3
1	54	18 zones	18 zones	18 zones
2	50	17 zones	17 zones	16
Total	104	35	35	34

3.1.5 Study Procedures

Once the community zones have been randomized, the research team and clinic staff will screen participants for eligibility at the health facility. This includes patients who are taking ART for at least 6 months or more and are clinically stable. If found to be eligible, the research team will explain the study and ask for written consent to take part in the study. The research team will then inform eligible participants which model they have been allocated to or whether they will continue to receive care at the facility. Participants allocated to one of the two community ART models will be offered a choice of whether they would prefer to receive this model or continue receiving care within the health facility. Participant choice will be recorded and participants opting for community ART delivery will be linked up with their respective CHiP teams to either register for a club or to start home delivery. Participants in these intervention arms may change their mind at any time either opting to move to the community model or to move back to the clinic model. Again this information will be recorded as an outcome measure

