3.1.1 Study Population

The eligible study population will include all stable HIV infected adult patients (≥ 18 years) on first-line ART residing in the 2 HPTN 071 communities and enrolled in the two primary health centres within the community. Stable patients are defined as those who are on first-line therapy, are on treatment and consistently retained in care for more than 6 months, virologically suppressed and have no other health conditions (e.g. TB, pregnancy and other opportunistic infections) requiring attention of a clinician.

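### Zones are randomised before patients are screened, and nothing keeps those who judge eligibility unaware of the zone's arm

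*Protocol*

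**What the plan says.** Section 3.1.4 states: "The community zones will be randomized by the research team to one of the three arms". An arm is a set of zones, so a patient's address determines the arm.

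Section 3.1.5 then gives the sequence. Screening follows randomisation: "Once the community zones have been randomized, the research team and clinic staff will screen participants for eligibility at the health facility". Next comes consent: "If found to be eligible, the research team will explain the study and ask for written consent to take part in the study". Only after that does the same section have the research team tell the patient the allocation. The protocol describes no blinding of screeners and no list of eligible patients fixed before allocation is known.

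A stable patient is described in three places:

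- Section 3.1.1: first-line therapy, retained for more than 6 months, virologically suppressed, and patients must "have no other health conditions (e.g. TB, pregnancy and other opportunistic infections) requiring attention of a clinician".
- Section 3.1.3: first-line treatment for more than 6 months and retained, virologically suppressed, WHO stage I or II. The item on other conditions is absent. Two further criteria are residence in the catchment area and being "Willing to provide written informed consent and accept CHiPs intervention".
- Section 3.1.5: "This includes patients who are taking ART for at least 6 months or more and are clinically stable".

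**The concern.** In a cluster trial, randomising zones balances the zones. It balances the patients only if they enter by a process that does not depend on the arm. Here patients enter after allocation, and residence, which determines the arm, is itself checked at screening. A screener who knows the arm can read the open-ended items more strictly in one arm than in another without breaching the protocol.

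Concealing the arm from the patient until consent is signed deals with patients who would join only for a preferred model. It does not deal with the person deciding whether the patient qualifies.

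The primary endpoint is death or non-suppression at 12 months. A small difference in baseline risk between arms therefore moves the primary comparison directly, and adding zones or participants would not remove that bias. Patients who were never enrolled cannot be recovered in the analysis.

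**Working it through.** **Inputs from the protocol (section 7.0).** Margin 5 percentage points; 35 zones per intervention arm and 34 control zones; 30 participants per zone; control failure 10% to 15% in the text, with 5% also in the table; coefficient of variation k of 0.25 to 0.30. The significance level is not stated. One-sided 2.5% is assumed because it reproduces the power table and one-sided 5% with the same variance formula does not.

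**Step 1: reproduce the stated power.** With p1 and p0 the failure proportions and d = p1 − p0:

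SE² = [p1(1 − p1)/30 + (k p1)²]/35 + [p0(1 − p0)/30 + (k p0)²]/34

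Chance of declaring non-inferiority = Φ((0.05 − d)/SE − 1.96)

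For p1 = p0 = 0.10 and k = 0.25, each bracket is 0.003 + 0.000625 = 0.003625. Then SE² = 0.003625/35 + 0.003625/34 = 0.000210, SE = 0.0145, and Φ(3.449 − 1.960) = 93.2%.

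| Control failure | k | Stated | Recomputed |
|---|---|---|---|
| 5% | 0.25 | 99% | 99.9% |
| 10% | 0.25 | 93% | 93.2% |
| 15% | 0.25 | 78% | 78.8% |
| 5% | 0.30 | 99% | 99.8% |
| 10% | 0.30 | 91% | 91.4% |
| 15% | 0.30 | 74% | 74.6% |

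The protocol's power figures stand. They assume no selection by arm.

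**Step 2: how far selection could move the failure rate (assumed inputs).** If a fraction f of candidates with failure risk r is screened out of a population with failure p, the remainder has failure (p − f r)/(1 − f). With p = 0.10 and r = 0.30, in intervention zones only:

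- f = 0.05: (0.10 − 0.015)/0.95 = 8.95%, a fall of 1.05 points, or 21% of the margin.
- f = 0.10: (0.10 − 0.03)/0.90 = 7.78%, a fall of 2.22 points, or 44% of the margin.

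**Step 3: effect on the false-claim rate.** Suppose the intervention is truly 5 points worse, so that the error rate should be 2.5%. Let selection lower observed intervention failure by b points. For control failure 10%, k = 0.25 and b = 1, p1 = 0.14, SE = 0.0160, and Φ((0.05 − 0.04)/0.0160 − 1.96) = 9.1%. Across control failure 10% to 15% and k 0.25 to 0.30:

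| b (points) | False non-inferiority |
|---|---|
| 0 | 2.5% |
| 0.5 | 4.3% to 4.9% |
| 1 | 7.0% to 9.1% |
| 2 | 16.6% to 24.8% |

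Applying the Step 2 formula at true intervention failure of 15% (control 10%), with f of 5% to 10% and r of 30% to 40%, the fall is 0.8 to 2.8 points and the false-claim rate about 7% to 44%. The width of that range shows how much depends on the assumptions.

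**Step 4: the opposite direction.** If the arms are truly equal and selection raises observed intervention failure by 1 point, power at 10% control failure and k = 0.25 falls from 93.2% to 76.7%.

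**The case against.** Several counter-arguments have force.

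- Most criteria can be read from records: regimen, time on ART, viral suppression, WHO stage and residence. It would be wrong to say that eligibility as a whole turns on judgement. The discretionary part is clinical stability and the open-ended item on other conditions.
- Section 3.1.3 says all adults on first-line ART are screened, Table 6 counts eligible patients who refuse, and section 5.0 collects baseline characteristics. These help, and baseline data could reveal imbalance on recorded items. They do not conceal the arm from screeners. No count of patients judged ineligible is specified by arm, and other health conditions are not among the listed baseline variables.
- A reader might infer that staff would hold doubtful patients back from the community zones and so push the result towards non-inferiority. Section 1.0 does list treatment failure and late referral among the risks of decentralised care. But section 3.1 gives decongestion of overburdened clinics as a reason for choosing these sites, which points towards freer enrolment in those zones. Sections 3.1.4 and 3.1.5 also let every participant there stay at the clinic or return to it, which weakens the motive for exclusion. The documents do not establish a direction.
- A reader might also infer that the individuals who randomise are those who screen. The protocol uses one collective term and does not say so. What it lacks is any provision for keeping the two apart.
- No passage supports the 5% to 10% held back or the 30% to 40% risk. Candidates must already be suppressed and retained, so a subgroup at three times average risk is an assumption. This objection stands, and the figures are illustrative only.

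**Conclusion.** The concern holds as a gap in the recruitment procedure. Allocation precedes screening, arm can be read from residence, screeners are not kept unaware of it, and the eligibility definition is not uniform. Recruitment could therefore differ by arm in either direction. Selection that favours non-inferiority is the more serious case for this design, but the documents do not show that it is the likelier one.

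The size is unknown. Under the assumed inputs the shift is about 1.1 to 2.2 points of the 5-point margin at 10% failure. With the significance level assumed one-sided 2.5%, a 1-point shift would raise the false-claim rate from 2.5% to between 7.0% and 9.1%. The stated power is not in error. Recruitment is fixed in section 3.1.5 and is not a matter for the statistical analysis plan.

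**What to change.** Amend section 3.1.5 as follows:

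1. Before the zone allocation is released to screening staff, draw from routine records a list of candidates in all zones who meet the recorded criteria: age, first-line regimen, time on ART, WHO stage, and viral load where available.
2. Screen everyone on the list against one eligibility definition. Sections 3.1.1, 3.1.3 and 3.1.5 must be reconciled to give it; which wording to keep is for the sponsor. State also what accepting the CHiPs intervention means for a patient in a control zone.
3. Add patients who become eligible later by the same recorded rule.
4. Look up the arm only after eligibility is recorded and consent is signed.
5. Record the numbers listed, screened, ineligible (with reason) and refusing, by arm.

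The cost is one data extract and a short delay before allocation is released. The extract needs linkage to zone, because the Smart care registration fields shown in Appendix III do not include it. Some viral loads may be missing and must then be resolved at screening. The judgement on other health conditions remains after the change: the log of ineligible patients makes it visible but does not remove it.

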4.0 Study Outcomes

The primary and secondary objectives for this study are listed in Section 2.2. The outcome measures for these objectives are listed below and will be measured in all study arms unless otherwise noted.

A. Primary Outcome – viral suppression at 12 months measured using the standard of care viral load testing equipment currently in place. Viral suppression will be defined according to National guidelines

B. Secondary Outcomes - these will include:

1. ***Viral suppression at 24 months*** – undetectable HIV viral load 24 months after entry into the models of care. This will be done as part of routine laboratory monitoring and measured using routine programmatic data.

2. ***Retention in care / Loss to Follow-up*** -Loss to follow-up from ART programmes describes all patients who are no longer in care and have an unknown outcome. A most useful definition of “loss to follow-up” should refer to patients with unknown outcomes(49). For this study, LTFU will be defined as “*no patient contact for 90 days or longer after the last given appointment*”.

Retention in care refers to *all patients retained in the HIV program*. Patients who are no longer retained in care with unknown outcomes will be classified as LTFU.

- In this study, retention will be defined as the number (%) of clients who are retained in the program at 6, 12 and 24 months after implementation of the intervention.
- The time to Lost to follow-up will be calculated in months according to the time interval between the dates of entry into the intervention to drop out, as recorded in the routine programmatic data.
- Proportion of patients that returned to mainstream care at 6, 12 and 24 months.

3. **HIV disease progression** – defined as having a new or recurrent WHO stage 3 or 4 condition after 6 months of ART, or a fall in CD4 count, (1). For patients with baseline CD4 count of < 200 cells/ μ l a fall of CD4 count to baseline or below after 6 months of ART; or persistent CD4 count < 100 cells/ μ l after 6 months of ART. (2). For patients with baseline CD4 count \geq 200 cells/ μ l, a persistent decline in CD4 count after two or more tests. For this study we will determine the following using routine health centre data:

- Proportion of patients who have had their CD4 count tests done at 6, 12 and 24 months after entering the models of care
- Proportion patients who developed a WHO stage 3 or 4 condition at 6, 12 and 24 months
- Proportion of patients with CD4 count below 200 at 6, 12 and 24 months despite on treatment.

4. Death – defined as death at any point during the intervention due to any HIV related cause after enrolment into the study.

5. Participant choice of model and retention within that model. The following outcomes will be measured using programmatic and routine health centre data:

- Proportion of patients who enrolled into the models of care by sex
- Proportion (%) of eligible patients but refused to enter the model of care at baseline
- Proportion of patients who switched back to mainstream care at 6, 12 and 24 months and reasons for switching
- Number of club sessions and home visits that took place at 12 and 24 months after start of intervention

6. Drug Supplies –using routine health centre and programmatic data, we will determine:

- Number of groups/individuals missing at least one refill in the last 12 and 24 months (ART, Cotrimoxazole)
- Missed dispensations of ARVs at 6, 12 and 24 months.
- Proportion of pre-packed drugs returned to the clinic after a club session or home-based visit.
- Number of reported cases of ART drugs being pilfered after the start of the intervention.

7. Qualitative evaluation- of the acceptability and functioning of the two models of community ART delivery based on systematic structured observations of delivery, in-depth interviews and focus group discussions with key-informants (CHiPs, health facility staff) and longitudinal interviews with PLWH.

8. Economic Analysis – this will include:

- Measuring and comparing the incremental costs of the two intervention packages. The economic analysis will focus on measuring economic costs of the interventions from provider's perspective. The main focus will be on costs to the health services, including personnel, equipment and materials. The incremental cost of the interventions will be estimated by comparing costs of service provision and healthcare utilization with non-intervention healthcare facilities.
- Measure the impact of implementing the community ART delivery models on health systems and service delivery at local health centres in terms of technical and allocative efficiency of available HIV resource.

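### Section 4.0 starts the clock for several all-arm secondary outcomes at entry into a model of care or the intervention, which contradicts the enrolment origin used elsewhere and gives clinic patients no start date

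*Protocol*

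**What the plan says.** Section 4.0 opens by stating that the outcome measures "will be measured in all study arms unless otherwise noted". The secondary outcomes that follow carry no note limiting them to the intervention arms, but they use several time origins:

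- B.1, 24-month suppression: "undetectable HIV viral load 24 months after entry into the models of care".
- B.2, time to LTFU: "the time interval between the dates of entry into the intervention to drop out".
- B.2, retention: number and percentage "retained in the program at 6, 12 and 24 months after implementation of the intervention".
- B.3, CD4 testing: patients who "have had their CD4 count tests done at 6, 12 and 24 months after entering the models of care".
- B.4, death: "due to any HIV related cause after enrolment into the study".

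Elsewhere the origin is study entry. The Study Duration entry of the Protocol Summary counts the 6-, 12- and 24-month secondary time points from recruitment. Section 7.0 counts the 12-month primary endpoint from study enrolment.

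Section 3.1.2 names two community models, adherence clubs and home-based delivery. Under Section 3.1.4, patients in Arm 3 zones stay with the clinic. Under Section 3.1.5, patients in the two intervention arms choose between the community model and the clinic after consenting, and may switch in either direction at any time.

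**The concern.** Secondary objectives 1 and 2 (Section 2.2.1) compare the community models with clinic care on 24-month suppression and LTFU. A between-arm comparison needs a time zero that exists for every randomised group and does not depend on what a patient does after enrolment. Model entry fails on both counts. Control patients never enter a model, and in the intervention arms the date depends on whether and when the patient takes up the offer.

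Time to LTFU is the most exposed, because it is an interval and cannot be computed without a start date. For late joiners, the clock would begin only after they had already stayed in care for some time. That earlier time at risk would be dropped in the intervention arms alone.

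**Working it through.** The plan gives no figure to reproduce on this point. Its power figures concern the 12-month endpoint counted from enrolment and do not use any of the disputed origins. The check is therefore a comparison of the passages, followed by a count of whom the wording reaches.

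**Step 1. Origins side by side**

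| Outcome | Place in protocol | Origin | Exists for a control patient? |
|---|---|---|---|
| Suppression, 12 months (primary) | Section 7.0 | Study enrolment | Yes |
| All secondary outcomes | Summary, Study Duration | Recruitment | Yes |
| Suppression, 24 months | 4.0 B.1 | Model entry | No |
| Time to LTFU | 4.0 B.2 | Intervention entry | No |
| Retention | 4.0 B.2 | Implementation | Yes, but a different origin |
| CD4 testing | 4.0 B.3 | Model entry | No |
| Death | 4.0 B.4 | Study enrolment | Yes |

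**Step 2. What Section 4.0 means by a model of care.** Item B.5 counts patients who enrolled into the models, those "eligible patients but refused to enter the model of care at baseline", and those who went back to mainstream care. A patient can therefore be in the study at baseline without having entered a model, and clinic care is what one returns to on leaving a model. On this usage, controls and patients who stay at the clinic have no model-entry date.

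**Step 3. Reach of the wording.** Section 3.1.4 gives 35 + 35 + 34 = 104 zones, of which 34 are control: 34/104 = 32.7%. With equal numbers of participants per zone (an assumption), that is also the share of participants without a model-entry date if every intervention-arm patient joins. If a fraction *u* of intervention-arm patients never joins, the share is (34 + 70*u*)/104. The protocol gives no value for *u*, so these are assumed values:

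- *u* = 0.1: (34 + 7)/104 = 41/104 = 39.4%
- *u* = 0.2: (34 + 14)/104 = 48/104 = 46.2%
- *u* = 0.3: (34 + 21)/104 = 55/104 = 52.9%

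These shares show how many patients the definition fails to cover. They are not estimates of bias.

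**Step 4. Late joiners.** Take a patient who joins a model *d* months after enrolment.

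- If lost *t* months after enrolment, with *t* > *d*, the literal time to LTFU is *t* − *d*, so *d* months at risk are left out.
- If lost before joining, the patient has no start date and drops out of the calculation.
- The 24-month point falls 24 + *d* months after enrolment. The Summary plans a study of about 24 months after implementation. For a patient enrolled at or after implementation, any *d* > 0 puts that point past the planned end, so the value may not exist.

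**Step 5. Who is not affected.** The visit schedule in Section 3.1.2 places enrolment into the club or home visits at month 0. For patients who accept at enrolment the origins coincide.

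**The case against.** The strongest reply is that the protocol uses its terms loosely and the intention is clear. Section 3.1.5 once speaks of a clinic model. Section 5.0 describes a baseline CD4 count as taken before enrolling into the models of care, as if that meant study entry. The title of the power table in Section 7.0 gives clinic patients a parallel start, namely continuing standard of care. Section 5.0 also sets common collection points at baseline and 3, 6, 12 and 24 months. Because the objectives require a comparison with clinic care, a sensible analyst would count from enrolment, and the statistical analysis plan may say so.

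Part of this stands. The intended origin is probably enrolment, and the loose usage softens the claim that clinic patients have no date at all. It does not repair the definitions. The power-table title covers only the 12-month endpoint, and Section 4.0's own use of the term in B.5 is the narrow one. This is also not a detail left to a later document: the protocol states an origin, and that origin conflicts with the others it states.

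A reader might infer more than the text supports:

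- *That the comparisons are biased towards the community models.* Step 4 shows effects in both directions: losses before joining disappear, while losses after joining get shorter times. Neither size nor direction can be determined from the document.
- *That LTFU and retention are undefined for controls.* LTFU status (no contact for 90 days or more after the last appointment) and being retained in the programme apply to everyone. Only the time to LTFU lacks a start. Retention from implementation needs no model-entry date; its fault is that it adds another origin.
- *That late joiners' viral loads would be taken well after month 24.* The planned study length argues against this. A missing value on that clock is the likelier result.

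**Conclusion.** Wrong as written, for secondary outcomes only. Section 4.0 applies its outcomes to all arms, yet times 24-month suppression, CD4 testing and time to LTFU from an event that control patients, and intervention-arm patients who stay at the clinic, do not experience. It times retention from yet another origin. This contradicts the Summary, Section 7.0 and its own definition of death.

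The wording leaves out at least the 34 of 104 control zones (32.7%), and more to the extent that intervention-arm patients never join. The conclusion rests on reading the models of care as Section 4.0 itself does in B.5. The late-joiner consequence also rests on the approximate study duration in the Summary. That limit would equally bind a patient enrolled after implementation on an enrolment clock, so the 24-month value may be missing rather than must be.

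The 12-month primary endpoint, its power and the primary conclusion are unaffected.

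**What to change.** In Section 4.0, define 24-month suppression, CD4 testing, retention and time to LTFU from the date of study enrolment in all three arms, whatever model the patient chooses or later joins. Use model-entry dates only for the uptake and retention-within-model measures in B.5. This brings Section 4.0 into line with the Summary, Section 7.0 and the definition of death in B.4. It also fits Section 8.2, which keeps patients who leave the intervention in the study.

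The cost is protocol wording. Under Section 3.1.5 every participant gives written consent before being told the allocation, so a date that precedes any choice of model should exist in every arm (assuming consent is dated in the usual way). No extra visits, tests or data extraction are needed.
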